Table 1. Power for effects of a single agent on specified endpoints in a factorial trial of 22,000 women and men, with 4 years of treatment and follow-up (#s in parentheses are expected number of events in both groups combined)

Observed RR *	True RR †	Total CVD	Total CVD + Mortality	Total Cancer	CVD death	Stroke	MI	Breast cancer
Placebo event rate (per 100 p-y)		3.0	5.0	2.2	1.0	0.9	0.8	0.8
0.90	0.875	76% (2479)	93% (4106)	63% (1837)	- (824)	- (743)	- (661)	- (661)
0.85	0.812	98% (2416)	>99% (4005)	93% (1790)	64% (803)	59% (723)	54% (644)	54% (644)
0.80	0.750	>99% (2353)	>99% (3903)	>99% (1743)	88% (781)	84% (704)	80% (627)	80% (627)
0.75	0.687	>99% (2290)	>99% (3801)	>99% (1695)	98% (760)	96% (685)	94% (609)	94% (609)
0.70	0.625	>99% (2226)	>99% (3697)	>99% (1648)	>99% (738)	>99% (665)	99% (592)	99% (592)
0.65	0.560	>99% (2162)	>99% (3592)	>99% (1600)	>99% (717)	>99% (646)	>99% (575)	>99% (575)

* Observed RR = intent-to-treat RR, including noncompliant participants and 80% compliance.

† True RR = that with perfect compliance.

- Power < 50%

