10.0. Statistical Analysis

In this 2x2 factorial trial, the primary aim is to compare the main effects of intention-to-treat with cocoa extract on incident CVD events, and multivitamins on rates of diagnoses of new cancers. The primary analysis will be based on the intention-to-treat principle and use the Cox proportional hazards model for time-to event data⁴¹ and estimate the HR for each intervention using indicators for the specific treatment, controlling for the second intervention, and stratifying the baseline hazard by (at minimum) sex, age group, and recruitment center (WHI or BWH). P-values will be based on a score tests for each intervention hazard ratio. Because the cohort consists of older women and men, competing risks due to deaths from other causes will be also be incorporated. Specifically, the primary analyses will estimate the cause-specific hazard and HR comparing intervention groups for each outcome by censoring individuals with deaths due to competing causes. We will estimate the cumulative incidence function for each comparison (multivitamin versus placebo, cocoa flavanols versus placebo) and plot the subdistribution of each endpoint over time.^{42,43}

The alternative Fine and Gray approach⁴⁴ models the effect of treatment on the subdistribution hazard or directly on the cumulative incidence function. Although we will consider this model, Cox proportional hazards will be our primary analysis. Additional analyses of composite endpoints that include total mortality will provide a practical approach to the evaluation of the impact of competing risks.

In secondary analyses, we will examine effect modification by the other randomized intervention, gender, age, other key risk factors, time, and concomitant medications such as statins and aspirin. Interactions will be interpreted cautiously as hypothesis generating. We will also stratify by past randomization status in WHI trials. We will also consider baseline dietary intake and a subcohort of women and men with biomarker data analyzed as a case-cohort study using methods for proportional hazards regression.⁴⁵ Because of frequency matching by age, we will use appropriate stratum-specific weighting of observations.⁴⁶

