The **CO**coa **S**upplement and
Multivitamin **O**utcomes **S**tudy
(COSMOS)
Statistical Analysis Plan

Investigators:

[name], DrPH and [name], MPH, Brigham and Women's Hospital

[name], Fred Hutchinson Cancer Research Center

February 4, 2022

ClinicalTrials.gov Identifier: NCT02422745

Infrastructure support provided by an investigator-initiated grant from Mars Symbioscience.

Cocoa Extract supplements and matching placebo provided by Mars Symbioscience.

Multivitamins and matching placebo provided by Pfizer Inc.

Partial infrastructure support provided through the National Heart Lung and Blood Institute's funding for the Women's Health Initiative Clinical Coordinating Center and Regional Center contracts.

COSMOS Statistical Analysis Plan

In this 2x2 factorial trial, the primary aim is to compare the main effects of intention-to-treat with cocoa extract on incident cardiovascular disease (CVD) events, and multivitamins on rates of diagnoses of new cancers. The primary analysis be based on the intention-to-treat principle and use the Cox proportional hazards model for time-to event data(1) and estimate the hazard ratio (HR) for each intervention using indicators for the specific treatment, controlling for the second intervention, and stratifying the baseline hazard by (at minimum) sex, age group, and recruitment center (Women's Health Initiative (WHI) or Brigham and Women's Hospital (BWH)). P-values will be based on a score tests for each intervention HR. Because the cohort consists of older women and men, competing risks due to deaths from other causes will also be incorporated. Specifically, the primary analyses will estimate the cause-specific hazard and HR comparing intervention groups for each outcome by censoring individuals with deaths due to competing causes. We will estimate the cumulative incidence function for each comparison (multivitamin versus placebo, cocoa extract versus placebo) and plot the subdistribution of each endpoint over time.(2, 3)

Cocoa extract-specific analyses

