Cox proportional hazards models estimated HRs using an indicator variable for cocoa extract treatment and stratifying the baseline hazard functions by sex, age group, recruitment source, and multivitamin intervention arm. COSMOS was designed for 22,000 participants with $\geq 80\%$ power to detect a 11% relative hazard reduction in total CVD, and $>95\%$ power to detect the same reduction for the secondary outcome of CVD plus all-cause mortality. We also had $\geq 90\%$ power to detect a 14% reduction in total cancer. Models were constructed for each clinical outcome, where person-time for each outcome was counted as days from randomization to the first post-randomization diagnosis of the designated outcome. Follow-up was censored at date of last contact, death, or end of the trial on December 31, 2020, whichever came first.

Kaplan-Meier cumulative incidence curves, cumulative HRs, interactions between randomization groups with trial-time, and analyses that excluded the first 1 and 2 years of follow-up assessed whether treatment effects varied over time (4). Nine subgroup analyses examined effect modification by *a priori* (concurrent multivitamin randomization assignment, sex, age, and use of statins or aspirin) and *post hoc* (history of CVD, smoking status, number of CVD risk factors, and chocolate consumption) factors. Secondary outcomes (n=14) mostly constituted subtypes of CVD or cancer. Statistical significance ($P \leq 0.05$) was assessed with two-sided p-values. We did not adjust P-values or confidence intervals for multiple testing. Consequently, results for secondary outcomes, other outcomes, subgroup analyses, and other analyses should be interpreted cautiously and considered hypothesis generating. At the nominal 0.05 level, we would expect less than one interaction and one secondary outcome to be significant by chance alone.

Per-protocol analyses censored follow-up when the participant discontinued trial pills, began outside non-study use of a cocoa supplement, and/or took <75% of study pills. HRs and 95% CIs were estimated using Cox regression models, weighted by the inverse probability of dependent-censoring for non-compliance (5). Additional analyses compared self-reports of non-monitored outcomes or potential side effects by intervention group. Analyses were performed using SAS 9.4.

Multivitamin-specific data analyses

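### Do the Kaplan-Meier curves in the SAP's agent-specific sections displace the competing-risk cumulative incidence that the plan promises?

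*SAP*

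**What the plan says.** Protocol section 10.0 notes that the cohort is old and says that "competing risks due to deaths from other causes will be also be incorporated". The primary analysis is a Cox model for the cause-specific hazard, with deaths from competing causes censored. For absolute risk over time, the SAP's opening section commits to a different estimator: "We will estimate the cumulative incidence function for each comparison (multivitamin versus placebo, cocoa extract versus placebo) and plot the subdistribution of each endpoint". It cites two competing-risk references for this, and Protocol section 10.0 makes the same commitment.

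The two agent-specific sections of the SAP are written in the past tense. Both state: "Follow-up was censored at date of last contact, death, or end of the trial on December 31, 2020, whichever came first". Both then name "Kaplan-Meier cumulative incidence curves, cumulative HRs, interactions between randomization groups with trial-time" as part of a list. In the cocoa section that list ends: "analyses that excluded the first 1 and 2 years of follow-up assessed whether treatment effects varied over time". The multivitamin section has the same list, with the early exclusion set at 2 years for cancer and 1 year for cardiovascular endpoints. Neither section mentions the cumulative incidence function or the subdistribution.

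**The concern.** When deaths from other causes are censored, one minus Kaplan-Meier is a transform of the cause-specific cumulative hazard. It is not the probability of having the event in a population whose members can die first. Calling it cumulative incidence gives it the name of the quantity that the opening section says will be estimated another way.

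The agent-specific sections describe what was done, while the opening section describes what will be done. A reader could infer that Kaplan-Meier replaced the cumulative incidence function. Absolute risks would then be overstated in both arms for every endpoint that does not include all-cause death. In a trial of women aged 65 or over and men aged 60 or over, that deserves a check.

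**Working it through.** **Inputs.** Protocol section 6.0, Table 1, gives placebo rates per 100 person-years of 3.0 for total CVD, 5.0 for total CVD plus mortality and 2.2 for total cancer. Mean follow-up is 4 years, with 22,000 participants split equally for each agent. Section 6.0 gives target reductions of 11% (CVD) and 14% (cancer), so HR 0.89 and 0.86.

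**The plan's own figures first.** Expected events at RR 0.90 are 11,000 × 4 × rate × (1 + 0.90).
- CVD: 11,000 × 4 × 0.030 × 1.90 = 2508 (Table 1: 2479).
- CVD plus mortality: 11,000 × 4 × 0.050 × 1.90 = 4180 (4106).
- Cancer: 11,000 × 4 × 0.022 × 1.90 = 1839 (1837).

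The power formula in section 6.0 gives Φ(√2479 × 0.10/1.90 − 1.96) = 74.6% for CVD, against 76% stated. The rates are therefore a sound basis for sizing the issue.

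**Competing death rate.** Cardiovascular death is already an event in the primary composite, so only death without a prior CVD event competes: 5.0 − 3.0 = 2.0 per 100 person-years. The documents give no such rate for cancer; I assume 1.5 to 2.5.

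**Formulas**, with constant hazards, event hazard h, competing hazard d (equal in both arms) and t = 4:
- 1 − KM = 1 − exp(−h·t)
- CIF = h/(h + d) × [1 − exp(−(h + d)·t)]

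For example, CVD on placebo: 1 − exp(−0.12) = 11.31%, and 0.03/0.05 × [1 − exp(−0.20)] = 10.88%.

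| Endpoint and arm | h | d | 1 − KM | CIF | Excess (points) |
|---|---|---|---|---|---|
| CVD, placebo | 0.0300 | 0.020 | 11.31% | 10.88% | 0.43 |
| CVD, active (HR 0.89) | 0.0267 | 0.020 | 10.13% | 9.74% | 0.39 |
| Cancer, placebo | 0.0220 | 0.015 | 8.42% | 8.18% | 0.24 |
| Cancer, placebo | 0.0220 | 0.025 | 8.42% | 8.02% | 0.40 |
| Cancer, active (HR 0.86) | 0.01892 | 0.015 | 7.29% | 7.08% | 0.21 |
| Cancer, active (HR 0.86) | 0.01892 | 0.025 | 7.29% | 6.94% | 0.35 |

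**Between arms.**
- CVD risk difference: 1.18 points by 1 − KM and 1.13 by CIF, a change of 0.04 before rounding. Risk ratio 0.896 by both.
- Cancer risk difference: 1.14 points by 1 − KM and 1.10 to 1.08 by CIF, a change of 0.03 to 0.05. Risk ratio 0.865 by both.

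**Sensitivity.** With d from 1.5 to 2.5 per 100 person-years, the CVD placebo excess runs from 0.33 to 0.54 points. At 5 years with d = 2.0 it is 13.93% − 13.27% = 0.66 points.

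**What the plan yields if followed.** The cause-specific Cox model censors competing deaths by design, so the choice of curve does not touch the hazard ratio or its score test. The opening section produces the cumulative incidence function for each comparison and says the team will "plot the subdistribution of each endpoint over time". The agent-specific sections add Kaplan-Meier curves beside cumulative hazard ratios, treatment-by-time interactions and early-exclusion analyses. All of these probe the cause-specific effect over time, for which one minus Kaplan-Meier is a legitimate display. The two instructions can both be carried out.

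**The case for a change.** The best case for a change is that a SAP should not leave two estimators under one name. An analyst working from the opening section would draw the competing-risk curve, and one working from the cocoa or multivitamin section would draw one minus Kaplan-Meier. Both could head the figure cumulative incidence, with different values, and readers tend to take such a curve as absolute risk whatever its stated purpose. The past tense of the agent-specific sections adds some weight, and the remedy would cost only a sentence and a relabelled or extra plot per agent.

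Part of this stands. The label is loose, and a cross-reference to the opening section would have been tidier. The rest is weaker. A general rule need not be repeated in each subsection of a short SAP, and silence does not withdraw it. The phrase names its estimator, and the censoring at death is stated just before it, so a statistical reader knows what was computed. The claim that readers will be misled depends on figure titles that the documents do not contain. The documents also specify no tabulated absolute risk, risk difference or number needed to treat.

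The plan has a further safeguard. Protocol section 10.0 uses composites that include total mortality to gauge competing risks, and section 5.2 makes CVD plus all-cause mortality a secondary outcome for both agents. No death competes with that endpoint, so the two estimators coincide there.

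**Conclusion.** No change to the plan is needed. The competing-risk cumulative incidence function is specified for both comparisons and is still in force. The Kaplan-Meier curves are an additional check on time-variation under an imprecise name.

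If those curves were taken as absolute risk, the 4-year placebo figure would be too high by about 0.4 points for CVD and by 0.24 to 0.40 points for cancer. Both arms would shift the same way, leaving 0.03 to 0.05 points in the risk difference. Hazard ratios, p-values and power do not depend on the curve, so no efficacy conclusion could turn on it.

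These sizes rest on the Table 1 planning rates, constant hazards and an equal competing death rate in the two arms. The cancer figures also rest on an assumed competing death rate of 1.5 to 2.5 per 100 person-years. Clearer labelling of the diagnostic curve is a matter for whoever prepares the figures.
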